## **9.3. AF ablation**

The patient will be admitted to the hospital on the morning of the procedure or on the night before the procedure, as per local SOP's. Apart from intra-procedural ICE/IVUS imaging, the AF ablations will be conducted in a completely standard fashion.

All AF ablations will be performed under general anaesthesia and on uninterrupted therapeutic anticoagulation with warfarin (target INR 2-3 in the last 3 weeks at least) or one of the new non-Vitamin K anticoagulant drugs. A heparin infusion will also be administered during the procedure with target Activated Clotting Time (ACT) values of 300-350 sec. Three-dimensional (3D) electro-anatomical mapping and/or fluoroscopy will be used by the operator, as usual, as anatomical guide during the procedure.

After general anaesthesia and oro-tracheal intubation, a trans-oesophageal echocardiogram (TOE) will be performed to rule out the presence of thrombus in the LA appendage.

Venous femoral access will be achieved and a deflectable decapolar diagnostic catheter placed to the coronary sinus. One or two atrial trans-septal punctures will be performed under TOE-guidance. The choice of the trans-septal kit (needle and sheath) and of the number of performed trans-septal punctures will be left to the operator.

Subject: Research protocol	Short Title: INSIDE PVs study	Chief Investigator: [name]
		Ethics Ref:
Version/Date: 1.0 /30 th June 2016	IRAS Ref: 156673	16/WM/0379
Page 16 of 29		

After the trans-septal puncture(s), pulmonary vein isolation (PVI) will be performed by using RF, cryo or laser energy as per operator's preference.

When using RF energy, the LA geometry will be reconstructed by using a 3-dimensional (3D) electro-anatomical mapping (EnSite Velocity or CARTO mapping system) and a multipolar circular mapping catheter (St Jude Medical Optima or Biosense Webster Lasso). Then a contact force ablation catheter (St Jude Medical EndosenseTacticath or Biosense Webster SmartTouch) through a deflectable sheath St Jude Medical Agilis will be used for PVI. The ablation sites will be annotated on the 3D electro-anatomical map. The choice of RF power, application time and mean contact force will be also left to operator preference.

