### **12.1. The Number of Participants**

This investigational study aims at building a model for real-time imaging of LA wall thickness and acute changes produced by catheter ablation for AF. As pilot study, it will enrol 12 patients elected to AF ablation with radiofrequency energy (4 patients), cryo-balloon (4 patients) or laser balloon (4 patients).

As each patient will undergo two cardiac CT scans (one before and after AF ablation), with LA wall thickness measurements in different locations, and repeated intra-procedural ultrasound imaging, with 1-2 acquisitions before and 1-2 acquisitions shortly after RF delivery for PVI in each PV, we expect that at the end of the study we will have enough information to confirm if intra-procedural ICE and/or IVUS are feasible for real-time imaging of the LA wall thickness during AF ablation and to streamline the CT protocol to a minimum dataset of acquisitions, with reduced radiation exposure. The study could also give us some insights about different mechanisms of lesion formation and different acute tissue changes caused by the different energy modalities, to be investigated further in a bigger randomized study.

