### **12.2. Description of Statistical Methods**

Comparison of primary, secondary and tertiary outcome measures among different treatment groups will be performed at each time point using appropriate statistical testing. In particular, ANOVA tests will be used to compare numerical variables and chi-square tests will be used to compare categorical values.

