### **12.3. Analysis of Outcome Measures**

Summary statistics, including means, medians, and variances, will be calculated at each time point and for each type of data (e.g. parameters derived from index AF procedure and follow-up visits).

If patients withdraw from the study we will analyse data already collected, unless the patients request otherwise. For every participant who withdraws, another participant will be sought in order to have a total of 12 full datasets for 12 participants.

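### Section 12.2 tests every outcome between three operator-chosen groups of 4 without error control or intervals, although the one energy comparison among the objectives calls for estimation

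*Combined protocol and SAP*

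**What the plan says.** Section 12.2 is the whole account of the statistical methods. It states that "Comparison of primary, secondary and tertiary outcome measures among different treatment groups will be performed at each time point using appropriate statistical testing", and that "ANOVA tests will be used to compare numerical variables and chi-square tests will be used to compare categorical values". It gives no significance level, no lead comparison, no adjustment for the number of tests and no confidence interval, and neither does any other section.

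Section 12.1 sets the size at 12 patients, 4 per energy, on pilot grounds. Section 9.3 leaves the choice of energy open: "RF, cryo or laser energy as per operator's preference". The groups are therefore not randomised.

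In the synopsis and section 6, only secondary objective 2 (percentage change in left atrial wall thickness with each energy) compares the energies. The primary objective compares ultrasound with CT, secondary objective 1 is feasibility, and secondary objective 3 is standardisation of CT. No tertiary outcome is defined. Section 12.1 presents the energy comparison as possible insight "to be investigated further in a bigger randomized study".

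Section 12.3 adds description: "Summary statistics, including means, medians, and variances, will be calculated at each time point". It does not say that these will be given by energy, and it attaches no intervals.

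**The concern.** The stated method does not fit the stated purpose. A pilot that hopes to inform a randomised comparison of energies has to deliver a difference and a spread, each with its uncertainty. Section 12.2 instead promises significance tests, and extends them from the one outcome that concerns energies to all of them, at each time point.

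Two misreadings become possible. With many unadjusted tests, one small p-value may be picked out as a signal when the energies do not differ. With 4 patients per group, a large p-value may be taken to show that they behave alike when the test could hardly have seen a difference. The documents propose neither reading, but section 12.2 does nothing to prevent them.

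**Working it through.** **The plan's own figure.** The only figure is 4 + 4 + 4 = 12. No significance level, power, effect size or SD is stated, so there is no calculation to reproduce. What follows describes how the stated plan would behave.

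**Inputs.** From the documents: three groups of 4 (section 12.1), ANOVA or chi-square (section 12.2), and the outcomes in section 6. Assumed: two-sided 0.05, no adjustment, one value per patient, effects in SD units.

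**1. Number of tests.** The documents give no list, so this one is illustrative.
- Thickness and diameter, by ultrasound and CT, before and after ablation: 2 × 2 × 2 = 8.
- Ultrasound minus CT, for thickness and diameter, before and after: 4.
- Percentage change in thickness, added procedural time, image quality: 3.
- Total: 15. Testing each of the 12 clock-face segments of section 9.7 separately would add more.

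**2. Chance of at least one false positive, k independent tests:** 1 − 0.95^k.
- k = 8: 33.7%.
- k = 13: 48.7%; k = 14: 51.2%, the first value above one half.
- k = 15: 53.7%.

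The 15 tests are not independent. Five are computed from the raw measurements (four differences and the percentage change), and the raw measurements are of the same walls and veins. I checked this by simulating the list with no true difference. Assumptions: 20% between-patient coefficient of variation; thickness independent of diameter; added time and image quality as independent continuous values. With correlations of 0.7 to 0.9 among the four measurements of each kind, the result is about 47% down to about 42%. If instead all 15 tests were equally correlated, it would be about 47% at correlation 0.3, 40% at 0.5, 30% at 0.7 and 17% at 0.9.

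**3. ANOVA power.** Noncentral F on 2 and 9 degrees of freedom, critical value 4.26, noncentrality λ = 4 × Σ(group mean − grand mean)².

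If one energy differs by d SD, λ = 4 × (2/3)d². If the means are evenly spaced over a range d, λ = 4 × d²/2 = 2d².

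| d (SD) | One energy differs | Evenly spaced |
|---|---|---|
| 0.5 | 8.8% | 7.8% |
| 1 | 21.8% | 17.3% |
| 2 | 69.0% | 56.0% |

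Power of 80% needs λ of about 13.7. That is d = √(13.7 × 3/8) = 2.27 if one energy differs, or d = √(13.7/2) = 2.62 if the means are evenly spaced.

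**4. Chi-square.** In a 3 × 2 table with 4 per group, the rarer category has an expected count of at most 2 per cell. By exact enumeration, the true type I error of the nominal 5% test is 0.5% to 5.1% for event rates of 10% to 50%. It is mostly conservative.

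**5. What estimation would give.**
- Pairwise difference, pooled SD on 9 df: half-width 2.262 × √(1/4 + 1/4) = 1.60 SD. Using only the two groups compared (6 df), it is 1.73 SD.
- 95% limits for the pooled SD: √(9/19.02) = 0.69 to √(9/2.70) = 1.83 times the estimate. For one group alone (3 df), they are 0.57 to 3.73 times.

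**The case against.** The best defence is that this is a declared pilot. The synopsis says so, and section 12.1 claims no more than possible insight into differences between energies. No confirmatory claim rests on the tests, so missing error control matters less than it would in a definitive trial. That stands, and it keeps the point modest. But section 12.2 does not label the tests exploratory, and pilot status is a reason to estimate rather than to test everything.

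Three stronger readings are tempting, and the documents do not support them.
- A reader might infer that the next trial would get no usable effect or spread. Section 12.3 plans means, medians and variances, and secondary outcome 2 is itself defined by energy. A mean, a variance and n = 4 yield an SD and any interval. What is missing is an explicit breakdown by energy and the intervals themselves.
- A reader might infer that a chance finding is more likely than not. That needs at least 14 independent tests. The illustrative list of 15 contains derived and correlated items, sparse chi-square tests mostly err on the conservative side, and neither the number of tests nor the significance level is stated.
- A reader might infer that a null result says nothing. Power is 69% when one energy differs by 2 SD, so a null result is some evidence against very large differences.

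It can also be said that three unadjusted pairwise intervals carry the same error rate as three unadjusted tests, that they will be very wide, and that pooling assumes equal variances, which 4 per group cannot check. All of this is true. The gain is that the imprecision is shown. A complete ban on tests would be partly a matter of preference, and the undefined tertiary outcomes are a clerical slip.

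**Conclusion.** The point holds as a mismatch between method and purpose. All outcomes are tested between three non-randomised groups of 4 with no lead comparison, error control or intervals, when only secondary outcome 2 concerns energies and it is meant to inform a later trial.

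The inflation of false positives is substantial but of uncertain size, because it depends on a test list and a dependence structure that the documents do not give. The low power is firmer: it depends only on the group sizes, the assumed 0.05 level and one roughly normal value per patient with equal variances. For differences of about 1 SD or less, a non-significant result is close to uninformative.

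This is an inexpensive improvement to a pilot's analysis text. It does not undermine the study's main aims.

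**What to change.** Revise section 12.2 as follows.

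- **Secondary outcome 2:** make estimation the stated analysis. Give the patient-level mean percentage change and SD for each energy, and the pairwise differences with 95% intervals. State whether the SD is pooled and, if so, that equal variances are assumed. Label the results non-randomised and hypothesis-generating.
- **Planning the next trial:** report the SD with a confidence interval, so that the next sample size is not built on a point estimate alone.
- **All other outcomes:** describe them by energy, and say so in section 12.3 as well.
- **Any between-energy test that is kept:** label it exploratory, and state that a non-significant result will not be reported as no difference.
- **Clerical:** remove the reference to tertiary outcomes, or define them.

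The change is to wording only. Patients, scans, procedures and sample size stay as they are. The downside is small: the report will carry fewer p-values, and its intervals, about ±1.6 SD for a pairwise difference, will look as wide as they are.

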## 5. STUDY DESIGN

Patients scheduled for their first pulmonary vein isolation ablation for symptomatic, drug-refractory paroxysmal AF, will be considered for inclusion in the study.

Potential subjects will initially be approached some weeks before their ablation procedure, in order to give the patients enough time to consider the information, to ask questions to the Investigator, their general practitioner (GP) or other independent parties to decide whether they wish to participate in the study or not.

For those interested in participation, a baseline assessment will be arranged to coincide with their standard pre-admission visit, for informed consent, screening and eligibility assessment. Moreover, a pre-operative imaging assessment with a cardiac CT scan will be performed to define the LA and PV anatomy and to measure the baseline LA wall thickness and PVs ostial diameters.

All AF ablation procedures will be performed in a standard fashion by using RF energy, cryo-balloon or laser balloon ablation under general anaesthesia (5) and with continuous oesophageal temperature monitoring. Ultrasound imaging by IVUS or ICE will be performed at sites corresponding with the PV/LA junction at the beginning and the end of the procedure in order to measure acute changes in LA wall thickness and PV ostial diameters.

The cardiac CT will be repeated within 24 hours post-procedure.

After the procedure, a pre-discharge review and a telephone follow-up at 1 week will be performed to identify any early and late complications related to the procedure.

A total of 12 patients will finally be enrolled in the study, 4 for each energy modality (RF, cryo and laser).

The end of the study for each patient will be the date of the telephone follow-up 1 week after the procedure.

For each patient the pre-procedural and post-procedural CT measurements of LA wall thickness and PVs ostial diameters will be compared with the corresponding IVUS or ICE measurements. Moreover, the acute tissue changes produced by the different energy modalities will be compared. Table 1 shows the main differences between the standard NHS process for AF ablation and the INSIDE PVs study appointments.

Standard NHS process for AF ablations	INSIDE PVs study appointments
Referral for procedure	Identification of participants

Subject: Research protocol	Short Title: INSIDE PVs study	Chief Investigator: [name]
Ethics Ref: 16/WM/0379		

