**Ethics Ref:**

16/WM/0379

**Version/Date:** 1.0 /30th June 2016    **IRAS Ref:** 156673

Secondary Objectives	Secondary Outcome Measure	
1. Feasibility of ICE/IVUS for real time imaging of the LA thickness and PV ostial diameters during AF ablation	1a. Additional procedural time 1b. Image quality	Day of AF ablation procedure
2. Comparison between acute tissue changes produced by RF, cryo and laser energy	2. Percentage change of LA wall thickness with each ablation modality (RF, cryo and laser energy)	Day of AF ablation procedure
3. Standardization of CT for LA wall thickness imaging with identification of a minimum dataset of acquisitions and reduction of radiation exposure	3. CT acquisitions associated to reproducible measurement of LA wall thickness with the lowest radiation exposure	Some days before and day after AF ablation procedure

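### With four patients per energy group, the chi-square test named in 12.2 cannot meet its usual conditions; an exact test should replace it (a minor point, confined to categorical secondary outcomes)

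*Combined protocol and SAP*

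**What the plan says.** Section 12.2 opens in general terms: "Comparison of primary, secondary and tertiary outcome measures among different treatment groups will be performed at each time point using appropriate statistical testing". It then becomes specific, naming ANOVA for numerical variables and adding that "chi-square tests will be used to compare categorical values". It gives no exact test, no rule for small expected counts and no significance level.

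The group sizes are fixed. Section 5 says "A total of 12 patients will finally be enrolled in the study, 4 for each energy modality (RF, cryo and laser", and section 12.1 repeats the split as "radiofrequency energy (4 patients), cryo-balloon (4 patients) or laser balloon (4 patients". Section 12.3 seeks a replacement for each withdrawal, so that the study ends with "another participant will be sought in order to have a total of 12 full datasets for 12 participants" or words to that effect for planning purposes: four complete datasets per group.

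The likeliest categorical outcome is in the section 6 table of objectives, where the feasibility measures are "1a. Additional procedural time 1b. Image quality". No scale or number of categories is given for image quality.

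**The concern.** The chi-square p-value is a large-sample approximation, and the usual working rule asks for expected counts of about 5. Here it is known before any data are collected that no patient-level table can satisfy that rule. The issue is whether the p-value reported for a particular observed table can be relied on. If it is well below the exact value, a between-energy difference in a categorical outcome could be reported as significant on evidence that an exact test would not regard as such. In a 12-patient pilot, a single patient can move the result across the line.

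**Working it through.** The plan has no power calculation or p-value to reproduce beyond 4 + 4 + 4 = 12.

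**Inputs.** Three groups of four (sections 5 and 12.1); chi-square for categorical comparisons (section 12.2). Assumed, because the documents are silent: a binary outcome measured once per patient, and alpha 0.05.

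**Step 1, expected counts.** With S of 12 patients having the outcome, each group's expected counts are S/3 and 4 − S/3. The largest possible value in a non-degenerate table is 11/3 = 3.67. With more categories, the expected counts in a group still sum to 4, so none reaches 5.

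**Step 2, two worked examples.** For a 3×2 table there are 2 degrees of freedom, so the chi-square p-value is exp(−X²/2). The exact p-value is the share of the C(12, S) equally likely arrangements that are at least as extreme.

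- *4/4, 1/4, 1/4.* S = 6, expected 2 and 2. X² = (4+1+1)/2 + (4+1+1)/2 = 6, so p = exp(−3) = 0.0498. The patterns with S = 6 at least as extreme are 4/2/0 (36 arrangements), 3/3/0 (48) and 4/1/1 (48). Exact p = 132/924 = 0.143. Ratio 2.87.
- *3/4, 0/4, 0/4.* S = 3, expected 1 and 3. X² = 6/1 + 6/3 = 8, so p = exp(−4) = 0.0183. Exact p = 12/220 = 0.0545. Ratio 2.98.

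**Step 3, all tables.** There are 33 distinct non-degenerate patterns. Nine have chi-square p < 0.05:

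| Events out of 4 per group | Chi-square p | Exact p | Exact p < 0.05? |
|---|---|---|---|
| 0/0/4 and 0/4/4 | 0.0025 | 0.0061 | yes |
| 0/1/4 and 0/3/4 | 0.0116 | 0.0303 | yes |
| 0/2/4 | 0.0183 | 0.0390 | yes |
| 0/0/3 and 1/4/4 | 0.0183 | 0.0545 | no |
| 0/3/3 and 1/1/4 | 0.0498 | 0.1429 | no |

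Four of the nine lose significance. The ratio of exact to chi-square p is 2.13 to 2.98 in these nine and 1.00 to 3.01 over all 33. It is below 2 in 13 of the 33. The maximum is at 2/4, 0/4, 0/4 (0.091 against 0.273). For these tables, ordering by probability or by the chi-square statistic gives the same exact p-value.

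**Step 4, more than two categories.** Enumerating 3×3 and 3×4 tables gives ratios of 0.35 to 3.20 and 0.10 to 2.79. Chi-square can therefore be too large as well as too small.

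**Step 5, error rate.** At a common event rate of 0.5, each of the 2¹² = 4096 outcomes is equally likely. The nine chi-square rejection patterns cover 12 + 3 + 24 + 132 + 24 + 3 + 12 = 210 outcomes (S = 3 to 9), and 210/4096 = 5.1%. The exact test rejects in 3 + 24 + 36 + 24 + 3 = 90, and 90/4096 = 2.2%. These are the maxima over the event rate. Conditional on S, the chi-square size is 132/924 = 14.3% at S = 6 and 12/220 = 5.45% at S = 3 or 9, and lower at every other S.

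**Step 6, unconditional exact test.** Ordering by X² and maximising over the event rate, 4/1/1 gives 210/4096 = 0.051. The 3/0/0 pattern gives 114/4096 = 0.028, counting only outcomes with X² of at least 8.

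**The case against.** The best defence is that chi-square does little harm here. Its overall error rate does not exceed 5.1%, and the 14.3% applies to one margin only. The design fixes the group sizes but not the number of patients with the outcome, so conditioning on both margins is a choice. An unconditional exact test is equally exact, and it puts 4/1/1 at 0.051 (chi-square 0.0498) and 3/0/0 at 0.028, which is no reversal. This stands, and it limits the point considerably.

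A second defence is that "using appropriate statistical testing" leaves room for an exact test. That carries less weight, because the next sentence names chi-square specifically. A change of test after the data are seen would be open to question.

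Third, image quality might be rated per vein or per pullback, since section 10.2 records each vein before and after isolation. Counts would then exceed four per group. That is possible, but those ratings would be clustered within patients, which is a different problem that an ordinary chi-square test does not solve either.

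Three stronger readings are tempting and not supported:

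- *Chi-square p-values here are too small by a fixed factor.* The ratio varies, equals 1 in some binary tables, and can fall below 1 with three or more categories.
- *The plan inflates false positives overall.* Step 5 shows that it does not, beyond 5.1% against an assumed 5%.
- *The planning of the larger study is at risk.* Section 12.1 links that study to mechanisms of lesion formation and acute tissue changes. The section 6 outcome for tissue changes is percentage change in wall thickness, which is numerical and falls under ANOVA.

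**Conclusion.** The point holds as a minor one. The named test is an approximation whose usual condition cannot be met in any patient-level table under this design. Its size, for a binary outcome at alpha 0.05, is a p-value up to about 3 times below the Fisher-Freeman-Halton value, with four of nine nominally significant patterns reversed. Both of those conditions are assumptions, as is analysis at patient level. The figures also depend on taking the conditional exact test as the comparator; the differences shrink under the unconditional one. The primary outcome, additional procedural time and percentage change in wall thickness are numerical and not touched.

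**What to change.** In section 12.2, replace the chi-square clause with wording such as: *patient-level categorical variables will be compared among energy groups with the Fisher-Freeman-Halton exact test, and counts will be reported with exact confidence intervals.* With four patients per group, the counts and intervals will tell the reader more than the p-value.

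This is one line of text and needs no extra patients or data. The statistical price is conservatism: p-values will be larger, by the two- to three-fold seen in the table for nominally significant binary results, and some power is lost. For a descriptive pilot that is a reasonable trade, but it should be acknowledged.
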